10 ADVERSE EVENT AND SERIOUS ADVERSE EVENTS

10.1 Definition of an Adverse Event (AE)

An AE is any untoward medical occurrence in a clinical study subject, temporally associated with the use of a study product including any washout or lead-in product (or medical device), whether or not considered related to the study product, including any washout or lead-in product (or medical device).

NOTE: An AE can therefore be any unfavorable and unintended sign (including an abnormal laboratory finding), symptom, or disease (new or exacerbated) temporally associated with the use of a study product including any washout or lead-in product (or medical device).

Events Meeting the AE Definition:

- Any abnormal laboratory test results (hematology, clinical chemistry, or urinalysis) or
 other safety assessments (e.g. ECG, radiological scans, vital sign measurements),
 including those that worsen from baseline, considered clinically significant in the
 medical and scientific judgment of the investigator (i.e., not related to progression of
 underlying disease).
- Exacerbation of a chronic or intermittent pre-existing condition including either an increase in frequency and/or intensity of the condition.
- New conditions detected or diagnosed after study product administration even though it may have been present before the start of the study.
- Signs, symptoms, or the clinical sequelae of a suspected drug-drug interaction.
- Signs, symptoms, or the clinical sequelae of a suspected overdose of either study product or a concomitant medication. Overdose per se will not be reported as an AE/SAE unless it is an intentional overdose taken with possible suicidal/self-harming intent. Such overdoses should be reported regardless of sequelae.
- "Lack of efficacy" or "failure of expected pharmacological action" per se will not be reported as an AE. Such instances will be captured in the efficacy assessments. However, the signs, symptoms, and/or clinical sequelae resulting from lack of efficacy will be reported as AE if they fulfill the definition of an AE.

Events NOT meeting the AE definition:

- Any clinically significant abnormal laboratory findings (if applicable) or other abnormal safety assessments which are associated with the underlying disease, unless judged by the investigator to be more severe than expected for the subject's condition.

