10.5.2 Assessment of Causality

The causality assessment is one of the criteria used when determining regulatory reporting requirements. For each AE (serious and non-serious), the investigator (or medically qualified designee) must provide an assessment of causality on the AE CRF page and the SAE form (subject to the classification of the AE). The investigator will also document in the medical notes that he/she has reviewed the AE and assessed causality, where applicable.

A "reasonable possibility" of a relationship conveys that there are facts, evidence, and/or arguments to suggest a causal relationship, rather than a relationship cannot be ruled out. Generally, the facts (evidence) or arguments to suggest a causal relationship should be provided.

The investigator will use clinical judgment to determine the relationship and will also consult the Investigator Brochure (IB), Safety Statement and/or Product Information, for marketed products, in the determination of his/her assessment. Alternative causes, such as underlying disease(s), concomitant therapy, other risk factors, and the temporal relationship of the event to the study product will be considered and investigated.

For each AE/SAE, the investigator must document in the medical notes that he/she has reviewed the AE/SAE and has provided an assessment of causality.

The investigator's assessment of causality must be provided for all AEs (serious and non-serious); the investigator must record the causal relationship in the CRF, as appropriate, and report such an assessment in accordance with the SAE reporting requirements if applicable.

There may be situations when an SAE has occurred, and the investigator has minimal information to include in the initial report to GSK. However, it is very important that the investigator always make an assessment of causality for every event prior to the initial

Protocol Number: 209638 Draft Clinical Protocol

transmission of the SAE data to GSK CH. The investigator may change his/her opinion of causality in light of follow-up information and send an SAE follow-up report with the updated causality assessment.

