To evaluate the impact of a post-treatment regression period of 6-days of no investigational product application on skin moisturization.	Change from baseline in Corneometer values at the following time-points: 
 • Day 30; • Day 31; • Day 32; • Day 33; • Day 34. (Face: area 1 compared to area 2; leg: area 5 compared to area 6).
To evaluate the impact of a repeated tape-strip challenge on skin barrier function following 4 weeks of twice-daily face and leg application of the investigational products and standard cleanser soap compared to the use of standard cleanser soap only.	Change from pre-challenge TEWL at Day 29 to the following time-points: 
 • Removal of 3 tape strips (face) and 4 tape strip (legs); • Removal of 6 tape strips (face) and 8 tape strip (legs); • Removal of 9 tape strips (face) and 12 tape strip (legs). (Face: area 3 compared to area 4; Leg: area 7 compared to area 8).
To evaluate the impact of a repeated tape-strip challenge on skin barrier integrity following 4 weeks of twice-daily face and leg application of the investigational products and standard cleanser soap compared to the use of standard cleanser soap only.	Total protein content extracted from all tape strips: (Face: area 3 compared to area 4; Leg: area 7 compared to area 8).
Safety	
To evaluate local tolerance.	Frequency and severity of adverse events (AE).

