1.3 Treatments

GlaxoSmithKline Consumer Healthcare (GSK CH) has developed two cosmetic moisturizer formulations intended to be suitable for use by consumers with dry skin, sensitive skin.

Subjects will be assigned to 1 of 2 treatment regimens in accordance with the randomization schedule.

- Treatment Regimen 1 = Test Product 1 + Standard cleanser soap; and Standard cleanser soap
- Treatment Regimen 2 = Test Product 2 + Standard cleanser soap; and Standard cleanser soap

To ensure balance across each side of face and legs, each eligible subject will be randomized to one of the following four arms:

- Test Product 1 + Standard cleanser soap (left); Standard cleanser soap (right)
- Test Product 1 + Standard cleanser soap (right); Standard cleanser soap (left)
- Test Product 2 + Standard cleanser soap (left); Standard cleanser soap (right)
- Test Product 2 + Standard cleanser soap (right); Standard cleanser soap (left)

The application quantity of the study products has been selected to reflect typical consumer usage of these types of products. The first application will be supervised by a trained technician when the subjects are at the study site. Subjects will be instructed to self-apply the study products at home, twice-daily (morning and evening) for 4 weeks.

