4.1 Populations for Analysis

4.1.1 Subject Disposition

Screen failures are defined as subjects who consent to participate in the clinical study but are not subsequently randomized. Enrolled subjects are defined as subjects who have signed the informed consent and are eligible to proceed beyond the screening visit.

A summary ([Table 14.1.1](#)) will be provided for number of subjects screened, number and percentage of screen failures with reasons why subjects are not randomized and number of subjects enrolled. Percentages for screen failure subjects will be based on total number of screened subjects.

Subject disposition will also summarize number and percentage of subjects in each of the defined analysis populations, who complete the study and who discontinue the study broken down by reason for discontinuation. The summary will be presented by treatment regimens [treatment regimen 1 (test product 1 + standard cleanser soap vs standard cleanser soap only), treatment regimen 2 (test product 2 + standard cleanser soap vs standard cleanser soap only)] and overall. The percentages are based on the total number of subjects randomized in each treatment regimen.

Subject disposition including the subject status (completer, Yes/No), demographic data (age, gender, and race), screening date, study product application start date and time, duration (in days) in the study (defined as [(date of completion or withdrawal – start date of study product application) + 1]), duration (in days) of study product (defined as: [(date/time of last product application - date of first product application) + 1]) and the specific reason for discontinuation, will be listed ([Listing 16.2.1.1](#)) by treatment regimen.

Subject disposition information for non-randomized subjects will include subject number, demographic information (age, gender, and race), screening date, reason for screen failure and details if any regarding the reason for screen failure ([Listing 16.2.1.2](#)).

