4.6.1 Adverse Events and Serious Adverse Events

All AEs will be reviewed by the Clinical Research Scientist or Designee prior to database lock and will be coded to a system organ class (SOC) and preferred term (PT) using the Medical Dictionary for Regulatory Activities (MedDRA). During this review stage, AEs will be further categorized as skin or non-skin.

Treatment emergent adverse events (TEAEs) are defined as new AEs that occur on or after the first treatment application (if this date is missing a suitable alternative will be used e.g., date of randomization). AEs with an onset date/time prior to the first treatment application will be considered as non-treatment emergent.

Summary of the number and percentage of subjects with at least one AE, total number of AEs, number and percentage of AEs within each SOC and PT will be displayed.

The treatment-related AE tables will be summarized by treatment arms (test product 1 + standard cleanser soap, test product 2 + standard cleanser soap, and standard cleanser soap alone); whereas, all other AE tables will be summarized by treatment regimen.

The listing of AEs will be provided by treatment regimen.

The following summary tables and listings will be presented by test product.

- Table of TEAEs by SOC and PT ([Table 14.3.1.1.1](#)).
- Table of TEAEs by Skin or Eye/Non-Skin or Non-Eye and PT ([Table 14.3.1.1.2](#))
- Table of TEAEs by SOC, PT, and severity ([Table 14.3.1.1.3](#))
- Table of treatment-related TEAEs by SOC and PT ([Table 14.3.1.2.1](#))
- Table of treatment-related TEAEs by Skin or Eye/Non-Skin or Non-Eye and PT ([Table 14.3.1.2.2](#))
- Table of treatment-related TEAEs by SOC, PT, and severity ([Table 14.3.1.2.3](#))

-
- Table of treatment-emergent serious adverse events (SAEs) by SOC and PT ([Table 14.3.1.3](#)) [only produced if there are more than 5 SAEs]
 - Table of treatment-emergent non-serious AEs by SOC and PT ([Table 14.3.1.4](#)) [only produced if there are more than 5 SAEs]
 - Table of TEAEs leading to study or treatment discontinuation by SOC and PT ([Table 14.3.1.5](#)).
 - Listing of all AEs ([Listing 16.2.7.1](#) for all randomized subjects; [Listing 16.2.7.2](#) for non-randomized subjects)
 - Listing of deaths ([Listing 14.3.2.1](#))
 - Listing of non-fatal SAEs ([Listing 14.3.2.2](#))
 - Listing of treatment-emergent AEs leading to study or treatment discontinuation ([Listing 14.3.2.3](#))

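### Among the SAP's adverse event tables, only those for treatment-related events separate cream from soap-only; local events judged unrelated enter no creamed-versus-soap summary

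*SAP*

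**What the plan says.** SAP section 4.6.1 fixes the columns of the AE tables. "The treatment-related AE tables will be summarized by treatment arms", and the three arms are test product 1 plus soap, test product 2 plus soap, and soap alone. The sentence then continues: "whereas, all other AE tables will be summarized by treatment regimen". AE listings are also by regimen.

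SAP section 1.3 shows what a regimen contains: "Treatment Regimen 1 = Test Product 1 + Standard cleanser soap; and Standard cleanser soap". It is the creamed side and the soap-only side of the same subject. SAP section 4.1.1 uses the term in the same way.

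The safety objective in SAP section 1.2 is "To evaluate local tolerance". Its endpoint is the frequency and severity of AEs, with no limit to related events. Protocol section 10.1 counts an event as an AE "whether or not considered related to the study product". Protocol section 10.5.2 says that a reasonable possibility of a relationship means there are "facts, evidence, and/or arguments to suggest a causal relationship, rather than a relationship cannot be ruled out".

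Two further statements matter. Protocol section 12.2.8 plans AE summaries for each test product. SAP section 4.6.1 also introduces its list of tables and listings as presented by test product, which matches neither the arm layout nor the regimen layout set just before it.

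**The concern.** Side is randomized within subject (Protocol sections 4.1 and 8.1.9), so for a local reaction the soap-only side is the design's own control. The summary tables use that control only for events that someone has already judged related to treatment. Because that judgement asks for positive grounds, a local event for which a relationship merely cannot be excluded may be classed as unrelated. It then goes into a column where the two sides are merged.

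At stake is the summary of local tolerance: whether creamed skin had more, or more severe, local events than soap-only skin in the same women. As planned, the tabulated answer depends on the causality call.

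**Working it through.** The plan gives no AE rate and no share of events expected to be related, so there is no stated figure to reproduce. The check is a reading of the display specification.

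**1. Displays side by side (SAP section 4.6.1)**

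| Display | Events covered | Columns | Cream and soap-only separated? |
|---|---|---|---|
| Tables 14.3.1.2.1 to 14.3.1.2.3 (by class and term, by skin/eye, by severity) | Treatment-related | Three arms | Yes, by arm |
| Tables 14.3.1.1.1 to 14.3.1.1.3 (same three breakdowns) | Any causality | Regimen | No |
| Listing 16.2.7.1 (all AEs) and Listing 14.3.2.4 (skin/eye) | Any causality | Regimen | Not stated |

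**2. Follow one local event.** If judged related, it is counted in both sets of tables, and the first set shows its arm. If judged unrelated, it is counted only in the second set and appears in the listings. No other readable section of either document gives an all-causality AE table by arm or by side.

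**3. What a regimen column can show.** Suppose the chance of at least one local event is p_c on the creamed side and p_s on the soap-only side, independently. The expected share of subjects counted in the regimen column is 1 − (1 − p_c)(1 − p_s). The rates below are assumptions chosen only to show the logic; they do not estimate the gap. The 75 subjects per regimen assume an equal split of the roughly 150 to be randomized (Protocol section 5.1).

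- p_c = 8%, p_s = 2%: 1 − 0.92 × 0.98 = 9.84%, or 75 × 0.0984 = 7.38 subjects.
- p_c = 2%, p_s = 8%: 1 − 0.98 × 0.92 = 9.84%, or 7.38 subjects.
- p_c = p_s = 5%: 1 − 0.95 × 0.95 = 9.75%, or 75 × 0.0975 = 7.31 subjects.

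An excess on the creamed side, the reverse, and no difference give practically the same column.

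**4. Bounds on what is lost.** In a regimen, let k subjects have a local event and r of them have at least one judged related. Then k − r subjects have only unrelated local events and enter no by-arm table. This runs from 0 (every affected subject has a related event) to k (none has). The documents give neither k nor r.

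**The case against.** The strongest reply is that the layout is sensible and breaks no promise. Many AEs have no side, so regimen columns suit all-causality tables, and arm columns suit events attributed to a product. The soap is itself a listed study product (Protocol Table 6-1), so a local event attributed to either cream or soap can reach the by-arm tables. What remains is local events attributed to neither, which bear least on product tolerance. Protocol section 12.2.8 asks only for summaries per test product, and the SAP already goes further with its soap-alone column. Protocol section 10.1 also keeps many likely reactions out of the AE data: responses that the dryness scale can describe are not usually AEs, and local tape-strip reactions count only if more severe than expected. All of this stands. It limits the point but does not answer it, because the endpoint is not confined to related events and the randomized control is available without a causality call.

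Stronger readings are tempting, but the documents do not support them:

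- *Unrelated local events are hidden.* They are counted in the regimen tables and appear in the listings. Side may be visible in those listings; the text does not say.
- *The plan has no side comparison of safety at all.* The related-event tables include a soap-alone column, for severity as well. The SAP does not say how an event is assigned to an arm, so even there it is an inference that arm means anatomical side.
- *The by-test-product sentence removes the soap-alone column.* Read alone it might, but the same section names three arms for the related tables. The two sentences need reconciling.
- *Causality will be judged by someone who knows the creamed side.* Protocol section 6.5 blinds the clinical examiner, and section 10.5.2 gives causality to the investigator or a medically qualified designee. The documents do not establish whether that person knows the side.

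The SAP's list of data displays (Attachment 1) is not readable here, so a further display cannot be ruled out.

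**Conclusion.** The point holds as a minor gap in the summary tables. Local events judged unrelated to treatment enter no creamed-versus-soap summary, although local tolerance is the only safety objective and the soap-only side is the within-subject control. The shortfall is against that objective. It is not a departure from the protocol's analysis section.

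Its size cannot be derived from the documents. It is nil if every subject with a local event has one judged related, and it may be small in any case given what Protocol section 10.1 leaves out. The conclusion rests on the column rule in SAP section 4.6.1 as written, and assumes that Attachment 1 adds no by-arm all-causality table. The primary efficacy analysis and its conclusion are unaffected.

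**What to change.** Add one descriptive table, without tests, of treatment-emergent skin/eye events located at the face or lower-leg application sites, by severity and regardless of causality. Its columns would be the test product 1 side, the test product 2 side and the soap-only side. Within each regimen, also count subjects with events on the creamed side only, the soap-only side only, or both. Show events without a known side as side not recorded. Keep all existing tables. In the same edit, reconcile the by-test-product sentence with the arm/regimen rule.

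The cost is one table shell and a few lines of SAP text. The table works only if the side or location of an AE is recorded or can be recovered from its description. The by-arm tables for related events suggest this, but the readable documents do not confirm it, least of all for unrelated events. Subjects also know which side they cream, so reporting bias remains. The table removes only the dependence on the causality judgement.

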4.6.2 Other Safety Variables

No other safety variables are applicable for this study.

4.7 Analysis of Other Variables

No other analysis will be performed in this study.

5 Changes to the Protocol Defined Statistical Analysis Plan

The changes from the originally planned statistical analysis specified in the protocol are outlined in [Table 5-1](#).

Table 5-1 Changes to Protocol Defined Analysis Plan

Protocol	Reporting & Analysis Plan	
Statistical Analysis section	Statistical Analysis Plan	Rationale for Changes
12.2.1 Definition of Analysis Populations PP Population The PP population includes all MITT subjects who fully comply with all study procedures and restrictions. Deviations will be determined and applied prior to unblinding and consist of variations in criteria likely to affect the interpretation of the efficacy parameters	4.1.3 Analysis Population PP Population All subjects in MITT population. All subjects comply with all study procedures and restrictions that may affect the interpretation of primary efficacy response. Deviations will be determined and applied prior to unblinding and consist of variations in criteria likely to affect the interpretation of the efficacy parameters	The definitions PP population in protocol was generalized. The definitions have been clarified and are now more study specific.

Attachment 1: List of Data Displays

GSKCH_209638_List
of TFLs v1.0_07Feb2
